#### **5.1.3.2 Concomitant Medication**

Concomitant medications are any prescription or over-the-counter preparations, including herbal products and “natural remedies”, used by a subject from time of informed consent to EOS visit. The medication name, start and stop date, route, dose and frequency and indication for each medication will be entered in the eCRF.

For all concomitant medications, from informed consent to EOS visit, the study site must provide an indication for its use. If the stated indication is a non-specific condition, e.g. “rash”, documentation of the condition, as specific as possible, should be recorded in the subject's clinical study records as source documentation.

## Supplemental Iron Use

### *Subjects receiving roxadustat*

#### *a. Oral iron*

Oral iron treatment is recommended for supplementation to support erythropoiesis and as first-line treatment for iron deficiency, unless the subject is intolerant to this treatment. The recommended daily dose is 200 mg of elemental iron. Subjects should be advised to take roxadustat at least 1 h before or 1 h after oral iron.

#### *b. Intravenous (IV) iron*

IV iron supplementation is allowed if all of the following criteria are met:

- The subject's Hb level has not responded adequately to roxadustat following 2 consecutive dose increases or reached the maximum dose limit, **and**
- The subject's ferritin is <100 ng/mL (<220 pmol/L) **or** TSAT < 20%, or the subject is intolerant of oral iron therapy.

Treatment with roxadustat should continue during IV iron administration. Discontinuation of IV iron administration is recommended once ferritin level  $\geq 100$  ng/mL ( $\geq 220$  pmol/L) and TSAT  $\geq 20\%$ . Serum ferritin and TSAT can be measured at any time after IV iron delivery at the discretion of the investigator.

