#### **1.4 Risk-Benefit Assessment**

The primary expected benefit of roxadustat is maintenance of Hb level within the recommended target range in subjects converted from ESA-based anemia treatment. Further, roxadustat may reduce anemia-related symptoms and signs, increase QoL, and reduce the need for IV iron therapy. Additional benefits include absence of a rise in blood pressure that is associated with ESA therapy, and a reduction in serum cholesterol level. Roxadustat is expected to be at least as safe as ESAs, and current data on surrogate outcomes suggest that cardiovascular risk may be lower than with ESAs.

An established dose adjustment algorithm, similar to the 1 used in phase 2 studies, will be applied for optimal roxadustat dose titration strategies. This allows correction and maintenance of Hb levels to the appropriate target range and facilitates close monitoring of Hb fluctuations over time.

Roxadustat doses may be held and the use of therapeutic phlebotomy is allowed in the event of clinical concerns for a subject's high Hb level. Per protocol, rules for the use of supplemental iron (oral or IV) and rescue treatments with epoetin alfa or darbepoetin alfa (roxadustat treated subjects only) and red blood cell transfusions are in place to assure subject safety in case of insufficient response to roxadustat treatment and/or acute need for correction of anemia.

In PK studies with roxadustat there was no evidence of drug accumulation with the proposed clinical regimen of 3 times weekly dosing. The overall frequency and nature of AEs and serious AEs (SAEs) observed in clinical studies generally reflect events what would be expected to occur in the CKD population (dialysis and nondialysis), and did not reveal any particular safety concern.

A drug interaction with statins is a potential risk. To mitigate this risk, recommendations for maximum statin doses are included in the study protocol. Also, the protocol includes a recommendation for the investigator to consider the posology of other concomitantly administered drugs that are substrates of the organic anion transporting polypeptide 1B1 (OATP1B1) and to refer to the SmPCs of these drugs.

Furthermore, there is a drug interaction with phosphate binders: concomitant intake of phosphate binders and roxadustat reduces the absorption of roxadustat.

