##### *Rescue therapy use:*

- Having received rescue therapy [composite of RBC transfusions (all patients) and rescue ESA (roxadustat treated subjects only)].
- Having received RBC transfusions.
- Number of RBC packs per subject.
- Volume of RBC transfused per subject.

*Iron use:*

- Having required IV iron supplementation.
- Mean monthly IV iron (mg) per subject during weeks 37-52 and weeks 53-104 (monthly defined as a period of 4 weeks).
- Having required oral iron supplementation.
- Mean monthly oral iron (mg) use per subject during day 1 to week 36, weeks 37 to 52, and weeks 53-104 (monthly defined as a period of 4 weeks).

*Changes in cholesterol levels, apolipoproteins*

- Change from BL to each postdosing study visit in
  - Total cholesterol.
  - LDL/High-density Lipoprotein (HDL) ratio.
  - Non-HDL cholesterol.
  - Apolipoproteins A1 and B.
  - ApoB/ApoA1 ratio.
- Occurrence of mean LDL cholesterol <100 mg/dL calculated over weeks 12 to 28.

*Blood pressure effect:*

- Occurrence of achieved antihypertensive treatment goal in CKD subjects (SBP < 140 mmHg and DBP < 90 mmHg) based on the mean SBP and mean DBP calculated over weeks 12 to 28.

*HRQoL and European Quality of Life 5 Domain 5 Level (EQ-5D 5L):*

- Change from BL to the average value of weeks 12 to 28 in
  - SF-36 Physical Component Score.
  - Anemia Subscale (“Additional Concerns”) of Functional Assessment of Cancer Therapy-Anemia (FACT-An) Score.
  - Total FACT-An Score.
  - EQ-5D 5L visual analogue scale (VAS) Score
- Patients’ Global Impression of Change (PGIC) (qualitative assessment)

*Hepcidin, Iron status, Glycated hemoglobin (HbA1c):*

- Changes from BL to each study visit (when measured) in:
  - Serum hepcidin
  - Serum ferritin
  - TSAT
  - Glycated hemoglobin (HbA1c) level

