### *Subjects receiving ESA*

For subjects treated with epoetin alfa or darbepoetin alfa, IV iron supplementation will be given according to standard of care.

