**Table 10 Key Secondary Endpoints Fixed Sequence Testing Procedure**

Test	Variable	Comparison
1	Proportion of Hb responders in the average of weeks 28 to 36 without having received rescue therapy. The non-inferiority margin for the difference between groups is 0.15.	Non-inferiority of roxadustat versus ESA
2	LDL cholesterol change from BL to the average of weeks 12 to 28.	Superiority of roxadustat versus ESA
3	Monthly IV iron (mg) use per subject during weeks 1 to 36.	Superiority of roxadustat versus ESA
4	SF-36 PF sub-score change from BL to the average of weeks 12 to 28. The non-inferiority margin is fixed as a difference of 3 points.	Non-inferiority of roxadustat versus ESA
5	SF-36 VT sub-score change from BL to the average of weeks 12 to 28. The non-inferiority margin is fixed as a difference of 3 points.	Non-inferiority of roxadustat versus ESA
6	MAP change from BL to the average MAP of weeks 20 to 28. The non-inferiority margin for the difference between groups is 1 mmHg.	Non-inferiority of roxadustat versus ESA
7	Time to an increase in blood pressure during weeks 1 to 36. The non-inferiority margin is fixed as a hazard ratio of 1.3.	Non-inferiority of roxadustat versus ESA

*Table continued on next page*

Test	Variable	Comparison
8	MAP change from BL to the average MAP of weeks 20 to 28.	Superiority of roxadustat versus ESA
9	Time to an increase in blood pressure during weeks 1 to 36.	Superiority of roxadustat versus ESA

1. The difference in the proportion of Hb responders in the average of weeks 28 to 36 between roxadustat and ESA will be calculated using the Miettinen & Nurminen [Miettinen et al, 1985] approach adjusting for the stratification factors. The null hypothesis will be rejected if the lower bound of the 2-sided  $100 \times (1 - \alpha^2)\%$  CI for the difference of proportions (roxadustat minus ESA) is greater than -0.15.
2. Change from BL in LDL cholesterol to the average value of LDL cholesterol of weeks 12-28 will be compared (roxadustat versus ESA) using an MMRM method including BL Hb value and other stratification factors as covariates. Superiority will be declared if the upper bound of the 2-sided  $100 \times (1 - \alpha^2)\%$  CI of the difference (roxadustat minus ESA) is lower than 0 mg/dL.

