6.1.3 Additional Secondary Efficacy Endpoints

The additional secondary efficacy endpoints are listed in [Table 6](#)

Table 6 Additional Secondary Efficacy Endpoints

Number	Endpoint
	Hb Maintenance
1	Hb response during weeks 28 and 36 defined as mean Hb – regardless of use of rescue therapy within the target range of 10.0 to 12.0 g/dL. Additional definitions to be included for sensitivity analyses are mean Hb \geq 10.0 g/dL during Week 28 and 36, during Week 28 and 52 and mean Hb between 10.0 and 12.0 g/dL during Week 28-52.
2	Hb change from BL to each post-dosing time point.
3	Hb level averaged over weeks 28 to 36, 44 to 52, and 96 to 104 without use of rescue therapy within 6 weeks prior to and during these 8-week evaluation periods.
4	Hb change from BL to the average Hb value of weeks 28 to 36, 44 to 52, and 96 to 104 regardless of the use of rescue therapy.
5	Proportion of Hb values \geq 10 g/dL and within 10.0 to 12.0 g/dL in weeks 28 to 36, 44 to 52, and 96 to 104 without use of rescue therapy within 6 weeks prior to and during these 8-week evaluation periods.
	Hospitalizations
6	Occurrence (number) of hospitalizations (HD days are not counted as hospitalizations, even when performed overnight), number of days of hospitalization per patient-year exposure and time to first hospitalization.
	Rescue Therapy Use
7	Occurrence and time to first use of rescue therapy [composite of RBC transfusions (all patients) and rescue ESA (roxadustat treated subjects only)], occurrence and time to first use of RBC transfusions, number of RBC packs per subject, volume of RBC transfused per subject.
	Iron Use
8	Occurrence of IV iron supplementation. Mean monthly IV iron (mg) per subject during weeks 37-52 and weeks 53-104 (monthly defined as a period of 4 weeks). Use of oral iron.
	Change in Cholesterol Levels, Apolipoproteins
9	Change from BL to each post-dosing study visit in Total cholesterol, LDL/High-density Lipoprotein (HDL) ratio, Non-HDL cholesterol, Apolipoproteins A1 and B, ApoB/ApoA1 ratio.
10	Occurrence of mean LDL cholesterol $<$ 100 mg/dL calculated over weeks 12 to 28.
	Blood Pressure Effect
11	Occurrence of achieved antihypertensive treatment goal in CKD subjects (SBP $<$ 140 mmHg and DBP $<$ 90 mmHg) based on the mean SBP and mean DBP calculated over weeks 12 to 28.
	HRQoL

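### Key secondary Test 3 compares IV iron use between arms with different iron rules, so it supports a strategy comparison and cannot by itself show a reduced need for IV iron

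*Protocol*

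**What the plan says.** **Roxadustat arm.** Protocol 5.1.3.2 (Supplemental Iron Use) puts oral iron first: "Oral iron treatment is recommended for supplementation to support erythropoiesis and as first-line treatment for iron deficiency". For the IV route, "IV iron supplementation is allowed if all of the following criteria are met". The first criterion is that the "Hb level has not responded adequately to roxadustat following 2 consecutive dose increases or reached the maximum dose limit". The second is ferritin below 100 ng/mL, or TSAT below 20%, or intolerance of oral iron. The synopsis has the same rule.

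**ESA arm.** The same section says that "IV iron supplementation will be given according to standard of care", with no further condition.

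**The test.** Protocol Table 10 lists as Test 3 "Monthly IV iron (mg) use per subject during weeks 1 to 36", for superiority. SAP 6.1.2.3 and 7.4.2.3 analyse mean monthly milligrams from day 1 to week 36 by ANCOVA on the FAS and count a subject with no IV iron record as 0 mg. Success is an upper 95% limit (roxadustat minus ESA) below 0. SAP Table 20 adds an All Randomized analysis (S1) and a time-to-first-IV-iron analysis (S2).

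**The benefit in view.** Protocol 1.4 says that roxadustat may "reduce the need for IV iron therapy".

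**Oral iron.** Protocol 2.3.3.1 lists "Mean monthly oral iron (mg) use per subject during day 1 to week 36, weeks 37 to 52, and weeks 53-104". SAP Table 6 has only "Use of oral iron", and SAP 6.1.3.8 derives it as yes or no by period.

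**The concern.** The endpoint is the amount of a treatment whose availability the protocol sets differently by arm. A lower total on roxadustat could come from the drug (better iron mobilisation), from the access rule, or from oral iron replacing IV iron. Test 3 cannot tell these apart. S1 and S2 are subject to the same rule, and no planned analysis puts the arms under a common one.

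Test 3 is a formal superiority claim in the key secondary sequence. If it succeeds, the natural reading is the benefit named in Protocol 1.4, which the comparison does not isolate. The change from oral milligrams to yes/no use removes the quantity needed to see how much oral iron stood in for IV iron.

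**Working it through.** The plan gives no effect size, SD or power for Test 3, so there is no figure to reproduce.

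**1. The rules side by side.** Take a subject with ferritin 60 ng/mL, TSAT 15% and a stable Hb of 11 g/dL.
- On roxadustat, below the dose cap: Protocol Table 4 gives no dose change at Hb 10.5 to <12.0 with a 4-week change within ±1.0. With no increases the first criterion is not met and IV iron is not allowed, although the second is met.
- On ESA: local standard of care decides.

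**2. When the first criterion can be met.** Scheduled adjustments start at week 4 and are 4-weekly (Protocol 5.1.2.1).
- Second consecutive increase: week 4 + 4 = week 8 at the earliest; 8/36 = 22% of the window.
- If response to the second increase is awaited for one more interval: week 12; 12/36 = 33%.

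There are exceptions.
- *Dose cap.* The cap is the dose step corresponding to 3.0 mg/kg, or 400 mg if lower. From the dose steps and the 45 kg entry minimum, a starting dose is already the top permitted step for 100 mg at 45 to <50 kg (150/3 = 50), 150 mg at 50 to <66.7 kg (200/3 = 66.7) and 200 mg at 66.7 to <83.3 kg (250/3 = 83.3). Read plainly, such subjects meet the maximum-dose limb on day 1, but still need the second criterion.
- *Hb below 9.0 g/dL.* One step up is allowed off schedule if there was no adjustment in the previous 4 weeks.
- *Low in-range Hb.* Table 4 prescribes an increase below 10.5 g/dL, so a subject at 10.0 to 10.4 is in the target range and can still accumulate increases.

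**3. Could the rule alone make Test 3 succeed?** This rests on assumptions, because the documents give no rates of IV iron use. Assume equal need in both arms and n = 375 per arm. A share q of ESA subjects uses IV iron, users have mean 1 (arbitrary unit) and coefficient of variation c, and the rule removes IV iron from a share b of would-be roxadustat users.
- ESA: mean q, variance q(1 + c²) − q². Roxadustat: the same with q(1 − b) in place of q.
- Chance of success = Φ(difference/SE − 1.96), with SE = √(sum of variances/n).
- Example, q = 0.4, c = 1, b = 0.5: means 0.40 and 0.20, variances 0.64 and 0.36, SE = √(1.00/375) = 0.0516, 0.20/0.0516 = 3.87, Φ(1.91) = 97%.

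If the rule only delays iron, every user keeps a fraction (1 − d) of the dose, with d = 8/36 or 12/36. Example, q = 0.4, c = 1, d = 8/36: difference 0.089, SE = √(0.64 × (1 + 0.778²)/375) = 0.0523, ratio 1.70, Φ(−0.26) = 40%.

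Ranges over q = 0.2 to 0.7 and c = 0.5 to 1.5:

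| Assumed effect of the rule | Chance that Test 3 succeeds with equal need |
|---|---|
| Delay of 8 of 36 weeks only | 14% to 97% |
| Delay of 12 of 36 weeks only | 28% to >99% |
| Removes 50% of would-be users | 52% to >99% |
| Removes 70% | 86% to >99% |
| Removes 90% | 99% to >99% |

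The nominal one-sided rate is 2.5%. With 300 per arm and 70% removed, the range is 77% to >99%. The SAP revision history (v3.0) remarks that most subjects used no IV iron, without giving the arm. Under pure delay, q is the same in both arms, so that remark points below 0.5. At q = 0.4 the 8-week range is 25% to 64%.

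**The case against.** The strongest reply is that Test 3 is worded as use, not need, and is a valid randomised comparison of two treatment strategies. It is reached only after Hb non-inferiority on the primary endpoint and on Test 1 (Hb response). Success would therefore mean that Hb was maintained with less IV iron, which is useful to know. The restriction also yields when Hb response is inadequate. Protocol 1.2.2.2 reports a dialysis study without IV iron in which Hb declined on epoetin and was maintained on roxadustat. Differing iron requirements are disclosed in Protocol 2.2.1.4 and SAP 3.3.

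All of that stands, and it defines what Test 3 can support. It does not close the gap to reduced need, because this trial does not show how ESA subjects would have fared under the same restriction.

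A reader might go further, in ways the documents do not support:
- *That the rule largely decides Test 3, or bars IV iron in nearly all roxadustat subjects.* No use rates are given, the modelled chance falls to 14% under pure delay, and the dose-cap exception covers ordinary adult weights.
- *That any subject with Hb in range is barred for all 36 weeks.* Table 4 and the dose cap contradict this.
- *That iron repletion at entry favours roxadustat.* It applies to both arms.
- *That Test 3 should leave the sequence.* An easily passed step does not inflate error for Tests 4 to 9, which keep their own level. Deleting a step late in an open-label trial would raise a multiplicity objection.

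**Conclusion.** The point holds as a limit on the conclusion. A significant Test 3 supports one statement: Hb was maintained with less IV iron under roxadustat, oral iron first and restricted IV iron, than under ESA with standard-of-care iron. It cannot by itself attribute the difference to a lower need for IV iron, and S1 and S2 carry the same limit. This follows from the text of the two iron rules and needs no assumption.

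The size is not fixed by the documents. The dose-increase route is closed until about week 8 of 36 by scheduled reviews, with earlier access for some subjects. The chance that the rule alone produces success runs from 14% to over 99%, depending on assumed use rates, variability and how far the rule removes rather than delays iron. Those figures show that the explanation is credible, not that it operates.

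**What to change.** Leave the iron rules and the test sequence unchanged.

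1. State in SAP 7.4.2.3 and in the CSR that the Test 3 claim concerns IV iron administered under arm-specific protocol rules, and is not evidence of reduced need. Apply the same wording to S1 and S2.
2. Restore the protocol's mean monthly oral iron endpoint in milligrams in SAP 6.1.3.8 and 7.4.3.8, in place of yes/no use. Dose, frequency and dates of concomitant medication are already recorded (Protocol 5.1.3.2). The SAP already counts users of IV and oral iron by period; what is missing is the amount, which is needed to size any substitution.
3. Optionally, tabulate by arm the proportion with ferritin below 100 ng/mL or TSAT below 20% at weeks 12, 20, 28 and 36. Both are collected at those visits, and SAP 7.4.3.14 already describes them by visit. Present this as context only: IV iron raises these indices, so the table is not independent of who was allowed it.

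The cost is that the sponsor must qualify one superiority claim and derive oral iron milligrams from concomitant medication records. No new data are needed.

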### *Subjects receiving ESA*

For subjects treated with epoetin alfa or darbepoetin alfa, IV iron supplementation will be given according to standard of care.

## Statins and Other Substrates for OATP1B1

There is a risk that roxadustat will increase the plasma levels of statins and other drugs that are substrates of OATP1B1, based on results from drug-drug interaction studies. Because statin dose has been known to be associated with the risk for side effects such as myopathy (e.g., myalgia, myositis and rhabdomyolysis), the investigator is advised to consider this potential interaction between roxadustat and statins when deciding on the appropriate dose of statins based on efficacy and safety of statin therapy. Switching to a non-interacting statin (e.g., pravastatin) may be considered. Furthermore, it is recommended not to exceed the proposed maximum daily dose of statins as outlined in [Table 5](#)

The investigator is also advised to consider this potential interaction between roxadustat and other drugs that are substrates for OATP1B1 when deciding on the appropriate posology of these drugs. Examples of these drugs are atrasentan, bosentan, ezetimibe, repaglinide, glyburide, SN-38 (active metabolite of irinotecan), rifampin, valsartan and olmesartan. It is recommended to refer to the SmPCs of these drugs for further details and guidance.

**Table 5 Proposed Maximum Daily Dose of Statins Not to be Exceeded in Patients on Dialysis**

Statin	Proposed maximum dose (mg/day)
Simvastatin	5
Atorvastatin	40
Rosuvastatin	Contraindicated
Fluvastatin	20
Pravastatin	40
Pitavastatin	1

### **Phosphate Binders and Other Multivalent Cation-containing Drugs and Mineral Supplements**

Results from a drug-drug interaction study demonstrated a significant reduction in roxadustat plasma exposure when a single dose of roxadustat was administered simultaneously with the phosphate binders sevelamer carbonate or calcium acetate.

Subjects should take roxadustat in a consistent manner relative to their phosphate binder intake, and discuss with the investigator before changing their phosphate binder dose or dosing time. To reduce the effect of phosphate binders on roxadustat exposure, subjects should take roxadustat at least 1 h before or 1 h after their phosphate binder.

It is anticipated that other multivalent cation-containing drugs and mineral supplements (e.g., iron, calcium, magnesium, aluminum), sucralfate or magnesium- or aluminum-containing antacids would produce a similar interaction; therefore, administration of roxadustat between -1 h and +1 h of intake of these preparations is not recommended.

### **Anti-hypertensive and lipid-lowering medication**

To avoid confounding effects on study endpoints, changes to anti-hypertensive and lipid lowering medications should be minimized as much as possible, and made only if deemed medically necessary by the investigator.

#### **5.1.3.3 Prohibited Medication**

The following medications are prohibited during the period identified:

- Any investigational drug: Within 30 days or 5 half lives or limit set by national law (whichever is longer), prior to the initiation of screening until EOS.
- Roxadustat or another hypoxia-inducible factor prolyl hydroxylase inhibitor: at any time prior to randomization. After randomization any hypoxia-inducible factor prolyl hydroxylase inhibitor other than roxadustat, as allocated by randomization, until EOS.
- Iron-chelating agents (e.g., deferoxamine, deferiprone, or deferasirox therapy): from 4 weeks prior to randomization until EOS.
- Androgens: From randomization onwards until EOS.
- Dapsone in any dose amount, or chronic doses of acetaminophen/paracetamol >2.0 g/day, from randomization until EOS.

Use of herbal medicines is discouraged during the course of the study.

#### 5.1.3.4 Procedure and non-drug therapy recording

Any other procedures or non-drug therapies need to be entered in subject's source documentation from informed consent until EOS and will also be recorded in the eCRF.

#### 5.1.4 Treatment Compliance

For subjects randomized to roxadustat, the quantity of study drug dispensed to and returned by the subject will be counted and recorded in the eCRF [Section 5.1.1]. If the subject is non-compliant with study drug intake, the investigator should discuss this with the subject. Deviations should be entered into the eCRF. All roxadustat bottles dispensed to the subject should be returned by the subject to the site (including empty bottles) at each study visit for reconciliation of returned tablet count by the study monitor.

For subjects randomized to ESA, the quantity of study drug dispensed and confirmation of administration will be recorded in the eCRF. All administrations will be performed by the investigator or a qualified member of the site staff or by the subject themselves or caregiver, e.g. relative, if well trained and willing to self-administer.

The quantity and dose of syringes dispensed to the subject and confirmation that all doses have been taken will be recorded in the eCRF. The empty outer packages of ESA with the unique kit number should be returned by the subjects and stored at site for reconciliation by the study monitor. Empty syringes need to be handled and destroyed according to local requirements.

